A clinical research coordinator will be trained to administer the Cancer and Aging Research Group's geriatric assessment (CARG GA) and healthcare provider assessments. Training for the geriatric assessment is available through the CALGB geriatric assessment instrument training website:

https://www.allianceforclinicaltrialsinoncology.org/training/auth/1%3A1%3A0%3A0%3A0/

A copy of the GA results may be made available to the patient's primary oncologist. Medical records may also be reviewed to determine if any actions were performed by the primary oncologist, as a result of the GA information (e.g.: a patient was identified to have nutritional concerns and on a subsequent visit a nutritionist was consulted).

4.5.3 PROMIS: Patient-Reported Outcome Measurement Information System Global Health Scale Short Form v1.1 HRQL measures provide invaluable information to the clinician regarding the patient experience of treatment or intervention. Large population based studies have demonstrated that patients with hematologic malignancy report some of the poorest HRQL.⁴⁸ However, exercise is reported to improve HRQL in cancer patients undergoing active treatment.⁴⁹ The PROMIS Global Health Scale has been rigorously tested for reliability and validity and can be applied to all populations.⁵⁰ It consists of 10 questions and will be self-administered to patients monthly. **[APPENDIX H]**

4.5.4 Falls

Falls in patients receiving chemotherapy are associated with a 3-fold greater risk of mortality.⁵¹ Fall and fall severity will be captured as self-report of calendar recorded falls, where patients denote on the calendar day when they had a fall associated with commentary on the event (e.g. fall with abrasion). Calendar recorded events is a valid method of self-reporting fall events and is shown to be more accurate than short term recall in patients with falls.⁵² Falls will be captured twice monthly. Research coordinators may contact the patient

by phone if a fall has occurred to identify the severity of the fall and/or injuries [APPENDIX I].

Inpatient admission falls will be captured per institution guidelines, as all falls are required to be reported to the Quality and Patient Safety Department. Specific information regarding patients enrolled in both as an Exercise Participant and Survey Participant will be gathered. Hospital Injury Level and the National Database of Nursing Quality Indicators (NDNQI) injury level will be captured.

4.5.5 Exercise Intervention: Otago Exercise Programme (OEP)

Exercise interventions are an established method of improving physiologic and functional performance in older adults. The structured OEP focuses on strengthening, balance retraining, and walking. OEP requires minimal training and can be provided by any physical therapist. OEP requires patient engagement and takes approximately 30 minutes three times weekly, with walking twice weekly. All physical therapist engaged in the protocol are OEP certified. The OEP is 8 physical therapy visits over 4 months. Participants will record daily of walking, exercise and falls in an exercise journal [APPENDIX J].

Patients may require more than 2 sessions monthly of physical therapy according to the physical therapist prescribed recommendations. In this event, exercise logs and fall diaries will be collected at their 1st and 3rd visit monthly. Patients will be reimbursed for their travel at these two visit times only (see Section 5.8).

Table 1. Otago	o Exercise Programme (OEP)				
	Strengthening	Balance Retraining	Walking		
Assessment			Timed Up and Go		
Activity	Five leg muscle strengthening exercises Four levels of difficulty	Twelve balance retraining exercises Four levels of difficulty	Advice about walking		
Intensity	Moderate Challenge 8-10 repetitions before fatigue	Moderate Challenge Each exercise at a level the patient can safely perform	Usual pace with usual walking aid		
Progressions	Increases from one to two sets Increase amount of ankle weight after 2 sets of 10	Supported exercise and unsupported exercise	Walk indoors Advance to walking outdoors when strength and balance have improved		
Length of Exercise Sessions	Approximately 30 minutes total for exercises; Exercises can be divided up over the day		30 minutes; can be split into three 10 minute walks throughout the day		
Home Based Frequency	3 times a week	At least 3 times a week	Twice a week		
Duration	Physical therapy (8 visits, twice monthly, until transplant or 4 months) Transplant physical therapy consult (twice weekly physical therapy consult during transplant admission). Home based exercise throughout their 6 month enrollment.				

4.5.6 OEP Evaluation

At the completion of the OEP, patients will be asked to indicate their likes and dislikes about the program, any logistical challenges, how worthwhile the program was to them personally, and ways in which the implementation of the program could be improved. Records will be kept of any patient adverse events during the course of the OEP [APPENDIX K].

4.5.7 Blessed Orientation-Memory-Concentration Test (BOMC)

The BOMC [APPENDIX L] is a widely used screening test for dementia and evaluation of orientation, registration, and attention. The test allows providers and caregivers to screen for suspected dementia in older patients. It was originally validated on older patients living in both skilled nursing facilities and community-dwelling. The BMOC is a weighted 6-item instrument and takes less than 10 minutes to complete. Scores range from 0-28, and scores greater than 10 are consistent with dementia.

Table 2. Study Measures					
	Study Visit 1: Baseline	Study Visit 2: Completion of OEP*	Study Visit 3: 6 months*		
CARG GA	Х	Х	Х		
SPPB	Х	X	Х		
PROMIS ^a	Х	X	Х		
Falls ^b	Х	X	Х		
OEP Evaluation		X			
Physical Therapy Adherence ^c		Х	Х		
Biomarker ^d	Х	X	Х		
Motivation	Х				
Self-Efficacy	Х	X	Х		
Barriers	Х	X	Х		
Blessed ^e	X*	X*	X*		

*(+/-)30 days; administered monthly; biomarkers (+/-) 14 days

a. PROMIS measures are captured monthly from the time of OEP enrollment (maximum 6 surveys)

b. Falls are captured twice monthly from the time of OEP enrollment via self-report calendar; inpatient falls are captured during hospitalization and are not a self-report.

c. Physical therapy adherence will be captured by the number of visits (inpatient and outpatient) and if patient is achieving the standard based upon the physical therapist assessment (1-achieving the standard, 2-progressing toward the standard, 3-limited progress or not meeting the standard)

d. Blood work will be collected during the study visit with the patients' outpatient hematologist. Attempts will be made to collect blood work during the routine draw, however this is not mandated. Biomarker collection (+/-) 14 days within study visit.

e. If not administered prior to patient's enrollment, the Blessed test will be administered one time at a point after the patient's enrollment in the study.

4.6 Potential Risks

We anticipate that this study will entail minimal physical and psychological risks for study participants. Informed consent will be obtained from all participants prior to study

enrollment. There is a small risk to participants of sustaining an injury while participating in the exercise intervention. Prior to participating in the intervention, all participants must have documentation from their primary oncologist or primary care physician stating that they are capable of participating in a moderate-intensity exercise intervention. There is a small risk of psychological distress associated with completion of the questionnaires. If this occurs, study staff will speak to the participant about the difficulties that the questionnaires have caused and will offer a referral to a mental health professional if necessary.

5.0 DATA COLLECTION AND MANAGEMENT

5.1 Registration Process

- Potential patient identified
- Patient signs informed consent and HIPAA form
- Eligibility Screening
- Worksheet documentation note by the primary oncologist giving the patient medical clearance to participate in physical therapy
- Provide patient with Enrollment Handbook [APPENDIX M]
- Register the patient on the study (Oncore)
- Assign a patient study number
- Pend blood work orders
- Documentation of Consent in EPIC
- Schedule twice monthly physical therapy sessions for next 4 months

5.2 Electronic Data Capture

5.2.1 iPAD Survey Administration: Many of the assessments are self-administered (CARG GA, PROMIS, Motivation, Self-efficacy and OEP evaluation) and, when possible, will be administered electronically. Some portions of the survey questionnaires are administered by a research coordinator (portions of the Barriers survey and CARG GA). Electronic administration will be done via an iPad. The questionnaires will be given within the context of routine clinical care. Patients will be provided with an iPad to complete the selfadministered surveys. The clinical research coordinator administers the functional and cognitive assessments. The feasibility of an iPad to electronically capture functional assessments requires additional information to determine practicality in an oncology setting. Patients unable to use an iPad or prefer not to use an iPad will have a paper survey options. Data on paper survey preference will be captured. Patients who choose to participate but then discontinue enrollment due to iPad use will be tabulated. In addition, the iPad questionnaire is a timed session and will be compared to published data for each questionnaire/battery to determine efficiency. Furthermore, data capture is complete; questionnaires were designed so one could not advance to the next question without a response including the option "I choose not to answer" for select sensitive questions.

5.2.2 Survey Software and Data Management: All data obtained via the iPad survey platform is supported by Qualtrics, a secure password protected online service. OSU Purchasing has contracted with Qualtrics to provide a single contract and OSU-managed single sign on to the cloud service for provisioning surveys for research at the university.

Qualtrics is the preferred survey tool at OSU and the only tool on contract. Information regarding Data Safety is linked here:

http://fisher.osu.edu/offices/technology/services/support-services/qualtrics

Patients will be enrolled into the Qualtrics survey platform system with a unique identifier code given to them during the registration process in OnCore. The unique identifier code linked to patient identification will be kept in REDCap. All protected health information will be kept in REDCap. REDCap is an electronic data collection (EDC) tool supported by the CCTS. It is a secure, web-based application designed exclusively to support data capture for research studies. Clinical data, and patient diaries will be captured in REDCap.

5.3 Baseline Demographic Questionnaire

Information will be collected on patient demographic information collected via a standard questionnaire administered at baseline and from IHIS

5.4 Clinical data to be obtained

Clinical follow-up for patients with hematologic malignancy will be performed according to the standard institutional guidelines. Clinical data regarding specifics of hematologic malignancy will be obtained from IHIS including but not limited to, diagnosis, date of diagnosis, stage, cytogenetics, prognostic information, treatment history, medications, physical exam parameters, hospitalizations, hospitalization length of stay, rehabilitation needs, bone marrow transplant length of stay, readmissions, transplant outcomes, hematologic and chemistry parameters e.g. CR, LDH, β 2-microglobulin.

Patients will be required to complete a follow up geriatric tool assessment at completion of the OEP, this may or may not be in context of a clinical appointment (+/- 30 days).

The following data will be collected from participants at baseline (Study Visit 1), post-OEP (Study Visit 2) and 6 month visits (Study Visit 3), and/or on a monthly basis

- Clinical Information
- CARG GA
- SPPB
- PROMIS HRQL
- Self- Efficacy Questionnaire
- Barriers
- Adverse events
- Motivation *(study visit 1 only)*
- OEP Evaluation (*study visit 2 only*)
- Physical Therapy Tracker [APPENDIX N] (every other physical therapy appointment)
- Physical Therapy Progress Tracking (study visit 2 and 3 only)

The following data will be collected from participants twice monthly at OEP appointments

• Walking, Exercise and Fall Diary

5.5 Adverse Events

Individuals will be asked about exercise-related adverse events at the time of study visit. Any exercise-related injuries will be reported to [name] (Principal Investigator). Any reported events will be evaluated for the likelihood that they occurred as a result of exercise. An adverse event is considered serious if it results in any of the following outcomes: 1.) death; 2.) a life-threatening event; 3.) inpatient hospitalization or prolongation of an existing hospitalization >24 hours; 4.) persistent or significant incapacitation or substantial disruption to the participants ability to conduct normal life functions; 5.) congenital anomaly/birth defect; 6.) Important Medical Events (IME) that may not result in death, be life threatening, or require hospitalization but may be considered serious when, based upon medical judgement, the event may jeopardize the patient and may require medical or surgical intervention to prevent one of the outcomes listed in the definition. Serious adverse events related to exercise experienced by patients in this protocol will be reported to the OSU CCC Clinical Trials Office and the Cancer Institutional Review Board (IRB). Information reported will include the number of patients affected, number of patients treated, summary of all adverse events reported to date using the National Cancer Institute Common Terminology Criteria for Adverse Events (CTCAE) version 4.0 grading, a specific list of adverse events requiring expedited reporting to include all serious adverse events [SAEs], and, on an annual basis or as it arises, significant literature reporting developments that may affect the safety of participants or the ethics of the study. Data safety and monitoring activities for each study will continue until all patients have completed their intervention and all patients are beyond the time point at which study-related adverse events would likely be encountered.

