1.2 Primary Objective

To assess the feasibility of implementing a structured exercise program by evaluating recruitment and retention, exercise program adherence, sustainability, adverse events, and implementation challenges.

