3.6 Study Procedures

A maximum of 100 patients will be recruited to the exercise protocol. Their participation will be supervised by a designated physical therapist (PT). Participants will meet with the PT at Martha Morehouse for their initial assessment and OEP instruction. The OEP will serve as a structured guide while providing education and motivation. Patients will undergo an initial assessment (short physical performance battery) measuring their strength, balance and gait as well as an individualized OEP based on their physical capacity and health. Patients will receive information on the rationale and benefit of exercise. The PT will ensure that the patient can perform the exercises correctly and safely, making adjustments as needed due to physical limitations such as pain and/or tolerance. The PT will provide home based instructions on exercise, assess patient safety during exercises, assess need for a walking aid, guide patient on appropriate footwear, fall education and exercise compliance, as examples of an OEP evaluation. The PT will monitor the program and provide appropriate advice on exercise progression based on patients' response to exercise. [APPENDIX B].

[figure not shown]
The patient will complete a total of 3 study visits, coordinated with the patients primary oncologist visit. The patient will complete study visit 1 prior to their first physical therapy appointment. The second study visit is at the completion of the OEP and the third study visit is at the end of study (6 months post-visit 1 or post-physical therapy appointment 1, whichever occurred first). These study visits may or may not be in context of a clinical appointment (+/- 30 days)

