6.0 STATISTICAL CONSIDERATIONS

6.1 Primary Endpoint

The primary endpoint is feasibility, defined by 80% of eligible participants completing the Otago Exercise Programme (OEP). Program completion is the primary indicator of this feasibility pilot project. 80% completion was chosen based upon the Otago Exercise Programme controlled trials, where the effectiveness of home based exercise to reduce falls in injuries in elderly adults in the community had a 90% completion rate of the trial.⁵³ When the Otago Exercise Programme was delivered in different centers 87% of participants

completed the trial⁵⁴. When the Otago Exercise Programme was introduced into the primary care practice, older adults (>80) approximately 47% participation occurred and 79% completed one year assessments 55. Therefore, 80% completion was chosen as the feasibility endpoint to achieve the desired effects of improving strength and balance via OEP.

We will describe the proportion of screened patients who agree to participate, the proportion of patients who attend certain percentage of assigned PT sessions and the proportion of patients who complete the whole study along with respective 95% confidence intervals. Study implementation and challenges will be evaluated by patient exercise logs. Exercise levels at home will also be assessed by exercise diary log. Adverse events (AE) and their severity will be captured according to the CTCAE v4.0, and whether any AEs can be attributed to exercise.

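### The only stated procedure for eliciting adverse events is tied to study visits and to exercise-related events, other sections conflict with it, and no adverse event contact is described for patients who leave the study

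*Combined protocol and SAP*

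**What the plan says.** Section 1.1 hypothesizes that the programme can be delivered safely. Section 1.2 makes adverse events part of the primary objective, which is met by "evaluating recruitment and retention, exercise program adherence, sustainability, adverse events, and implementation challenges".

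The passages on how adverse events are obtained differ:

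- **Section 5.5** is the only one that describes questioning the patient: "Individuals will be asked about exercise-related adverse events at the time of study visit". Reported events are then judged for relation to exercise. Expedited reporting covers serious events related to exercise.
- **Section 4.5.6** is wider and continuous: "Records will be kept of any patient adverse events during the course of the OEP".
- **Section 5.4** puts adverse events in a list whose heading allows collection at the three visits, monthly, or both. It does not say which items are monthly.
- **Section 6.1** has events graded by CTCAE v4.0 and then a judgement of "whether any AEs can be attributed to exercise".
- **Table 3** marks adverse events at visits 1, 2 and 3, also with attribution after capture.

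On the visits, section 3.6 states: "The patient will complete a total of 3 study visits". It adds: "The patient will complete study visit 1 prior to their first physical therapy appointment". Visit 2 falls at completion of the programme and visit 3 at 6 months. Falls follow a separate route (4.5.4, 5.4, Table 2): a calendar diary captured twice monthly, with institutional reporting for inpatient falls. Section 5.7 gives the grounds for removal from study and describes no adverse event contact at that point.

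**The concern.** A site that follows section 5.5 to the letter asks each patient twice, at visits 2 and 3, about harms that could have come from the programme. It asks only about events the patient already links to exercise. Patients under treatment for a hematologic malignancy are poorly placed to make that judgement first. An event they put down to chemotherapy or disease would not be solicited, so the attribution step in 6.1 might never see it.

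The protocol has itself accepted the argument against recall, for falls: "Calendar recorded events is a valid method of self-reporting fall events and is shown to be more accurate than short term recall". It does not carry that reasoning over to strains, pain, syncope or other non-fall events.

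Visit 2 is also defined by completing the programme. A patient who stops because of an injury or illness has no defined visit 2, and one who leaves the study is not asked again under any procedure described. What is at stake is the safety part of the primary objective: the reported rate could look better than the truth because of who is asked, and when.

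**Working it through.** The plan gives no figure for this point, so the check is a comparison of passages plus the recall intervals that follow from the visit schedule.

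**Inputs.** Three visits, the first before physical therapy starts (3.6). Eight physical therapy sessions over 4 months (4.1, 4.5.5). Visit 3 at 6 months (3.6). Visit window of 30 days either side in 3.6 and Table 2, but 45 days in Table 3. Diary and falls capture twice monthly (4.5.4, 5.4). One month is taken as 365.25/12 = 30.44 days.

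**Step 1: visits that can detect harm from the programme.** Three visits less visit 1 leaves two.

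**Step 2: recall interval at visit 2.** This assumes that physical therapy starts soon after visit 1 and lasts the stated 4 months. The window is applied to visit 2 only.

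| Case | Days | Months |
|---|---|---|
| Nominal | 4 × 30.44 = 121.75 | 4.0 |
| 30-day window | 121.75 ± 30 = 91.75 to 151.75 | 3.0 to 5.0 |
| 45-day window | 121.75 ± 45 = 76.75 to 166.75 | 2.5 to 5.5 |

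Nominally, visit 2 to visit 3 is 2 × 30.44 = about 61 days.

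**Step 3: comparison with falls.** Twice-monthly capture means one capture every 30.44/2 = about 15 days. The nominal recall interval for other events is 121.75/15.22 = 8 times as long.

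**Step 4: patients who stop early.** Visit 3 is timed from visit 1 or the first therapy appointment, not from completion (3.6). Under 5.7 patients remain on study for 6 months unless removed by preference or at a physician's request. There are therefore two groups:

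- Stops the programme, stays on study: next asked at visit 3, nominally 6 × 30.44 = about 183 days after visit 1.
- Leaves the study: no further adverse event contact is described.

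**Step 5: direction of the bias.** Let *p* be the share of patients who leave the study without being asked, *r1* their event rate and *r0* the rate in everyone else. The true rate is (1 − *p*)*r0* + *p r1*.

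- With all enrolled patients as denominator, the rate seen is (1 − *p*)*r0*, so the shortfall is *p r1*. This is downward whenever any of those patients had an event that was not otherwise captured.
- With only those asked as denominator, the rate seen is *r0*, so the shortfall is *p*(*r1* − *r0*). This is downward if those who leave had more events than those who stay.

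The documents give none of *p*, *r1* and *r0*, so no size can be put on it.

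**Step 6: do the other sections settle the matter?** On frequency, the list in 5.4 that names adverse events also names the geriatric assessment and the SPPB. Sections 4.5.1 and 4.5.2 provide for these at baseline, programme completion and 6 months, as does Table 2. The monthly wording therefore cannot apply to every item, and it does not establish monthly questioning about adverse events. Section 4.5.6 says records are kept, but names no question, time or person, and it sits in a section on an evaluation done at completion. On scope, 4.5.6, 6.1 and Table 3 expect events in general with attribution afterwards, while the question in 5.5 is confined to exercise-related events. Nothing in the documents ranks one section above another.

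**The case against.** The strongest reply is that 5.5 is one narrow sentence in a wider scheme. Section 5.4 permits monthly collection, and 4.5.6 promises records of any event during the programme. Section 6.1 and Table 3 capture events and then attribute them, and 5.5 itself later refers to a summary of all adverse events. Falls, a key harm of an exercise programme, are recorded prospectively, captured twice monthly and may be followed up by telephone. Hospitalizations and readmissions are taken from the medical record (5.4). The therapist assesses safety and adjusts for pain (3.6), session notes record non-participation and its reason (4.1), and the coordinator asks about problems with home exercise (4.3).

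Much of this stands. A reader might infer from 5.5 that adverse events are collected only at the three visits and only if exercise-related. The documents do not support that, because 4.5.6, 5.4, 6.1 and Table 3 all say something wider. They show an unresolved conflict, with the most specific instruction being the narrowest.

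A reader might also infer from the 80% completion criterion that up to 20 of 100 patients would never be asked. That does not follow either: the criterion concerns completing the programme, and a non-completer who stays on study still has visit 3.

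What the reply does not supply is a stated question, at a stated time, for non-fall events between visits, or any contact when a patient leaves the study. The therapist and coordinator contacts are not described as a means of recording adverse events. Appendices B, J, K and N are not in the text reviewed, so adverse event fields on those forms cannot be excluded.

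**Conclusion.** The point holds as a conflict between sections and a gap in ascertainment. Under the only stated elicitation procedure, non-fall events that do not lead to a recorded hospitalization may rest on about 4 months of recall at visit 2. At the end of the window this becomes about 5 months (3.6 and Table 2) or about 5.5 months (Table 3), against about two weeks for falls. Patients who leave the study have no adverse event contact described, so events behind early withdrawal can be missed and the rate biased downward. The direction is plausible; the size cannot be derived from the documents.

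This rests on three assumptions: that sites follow 5.5 as written, that the forms not seen do not already ask the question, and that visit 2 falls about 4 months after visit 1. It does not show that safety as a whole depends on recall, since falls and hospitalizations have their own sources. The change is a worthwhile low-cost improvement; the design does not fail without it.

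**What to change.** In section 5.5, replace the visit-based question with a brief open question about any adverse event, asked at the existing twice-monthly therapy or diary contacts and once at withdrawal, by telephone if needed. Record each event with its date on the diary form. Have the study team, not the patient, assign relation to exercise afterwards. Align 4.5.6, 5.4, 5.7, 6.1 and Table 3 so that they state one frequency and one scope, and add the withdrawal contact to 5.7.

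The cost is protocol wording and a line on an existing form, plus a few minutes at contacts that already take place and one call for those who withdraw. In this population the open question will also bring in more disease- and treatment-related events to record and attribute.
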